2.2.2 Randomisation

Approximately 110 male and female children from 1 month to 17 years of age, with iron deficiency anaemia at approximately 20 sites will be recruited. The number of subjects will be reduced if the study is stopped following a successful interim analysis.

Subjects aged 2 to 17 years will be 1:1 randomised to ferric maltol and ferrous sulfate, with 49 subjects in each arm. Subjects then will be further divided into 2 age groups: 2 yrs – 9 yrs and 10 yrs -17 yrs. A minimum of 18 subjects must be recruited into the 2 yrs - 9 yrs and 10 yrs – 17 yrs age groups across the study as a whole and a minimum of 25% of either sex must be recruited.

A maximum of 12 subjects will be recruited in the 1 month to less than 2 years age group.

2.2.3 Study Drug

Subjects will be instructed to take the study drug as described in detail on the drug labels and by the investigator/designee.

Ferric maltol group:

Subjects aged 1 month to 17 years randomised or assigned to oral ferric maltol will receive the following dosing for the duration of the study (12 weeks), including 2 PK days:

Age	Dose	Suspension equivalent
1 month to < 2 years	0.6 mg/kg/dose, BID	0.1 ml/kg/dose, BID
2 years to 11 years	15 mg per dose, BID	2.5 ml per dose, BID
12 years to 17 years	30 mg per dose, BID	5 ml per dose, BID

Ferrous sulfate group:

Ferrous sulfate oral liquid 125 mg/ml (25 mg/ml elemental iron) or equivalent dose will be used for all children/adolescents randomised to this group.

Subjects aged 2 years to 17 years randomised to oral ferrous sulfate will receive the following dosing for the duration of the study (12 weeks):

0.24ml per kg body weight, up to a maximum of 8 ml given daily in two divided doses.

Age	Dose	Liquid equivalent
2 years to 17 years	3 mg/kg/dose, BID	0.12 ml/kg/dose, BID

In the event of an administered dose not being consumed or partially consumed, in either treatment group, by the patient this will be noted as a missed dose and will not be repeated. Clear instructions will be provided to the parents/guardians who are supervising the drug administration and dosing diary.

Patient weight should be recorded at each clinic visit and drug dosing administered as per last clinic visit weight.

Subjects (ferric maltol and ferrous sulfate) will be instructed on Visit 2 to complete a dosing diary from the evening of Visit 2 until the next visit, in order to document the day and time that they took their morning and evening doses on those treatment days whilst at home. Subjects will be instructed to return all unused supplies medication packaging on their visits, having withheld their dose of ferric maltol on PK Day 2 morning. Compliance will be assessed from the dosing diary entries and reconciled using the drug accountability form.

If a subject is found to be non-compliant with the study medication (defined as less than 80% or more than 120% compliant with the dosage schedule), the subject/parent/legal guardian will be counselled and trained on the importance of maintaining adherence to study medication. If the subject is repeatedly non-adherent, a decision will be made by the medical monitor and/or Sponsor as to whether the subject should be withdrawn from the study treatment.

2.2.4 Sample Size Determination

In total up to 110 patients will be recruited into the study. Up to 98 subjects will be randomised in the 2 -17 years cohort and up to 12 subjects will be assigned in the <2 years cohort.

The aim is to recruit up to 49 subjects in each treatment group in the 2 – 17 years cohort. At least 12 subjects in each age group respectively (i.e. 24 subjects in total) will be included in the PK analysis group in the ferric maltol oral suspension group. A sample size of 49 in the Ferric Maltol group provides at least 80% power to demonstrate that the lower bound of the 95% confidence interval for increase in Hb at 12 weeks, compared with baseline, is above zero. This assumed that the standard deviation (SD) of the change from baseline is 1.2 g/dL or lower and the true mean change is at least 0.5 g/dL.

Every effort will be made to recruit up to 12 subjects in the under 2's age group but in case of reasons of feasibility it cannot be completed, then the study may be completed without that cohort.

If less than 91 subjects in total have been randomised when 32 ferric maltol subjects have completed treatment (or withdrawn from the study), then an interim analysis of the primary effectiveness endpoint (change in Hb concentration from baseline to Week 12) will be conducted. If significant, the study will stop recruitment. If not significant, the study will continue (all subjects will be assigned to ferric maltol) until 54 subjects have been recruited in the ferric maltol arm.

2.3 Study Endpoints

2.3.1 Primary Endpoints

- Safety and gastrointestinal tolerability:
 - Treatment-emergent Adverse Events (TEAE),
 - o Treatment-emergent Serious Adverse Events (TESAEs),

- Treatment-emergent Adverse Events leading to premature discontinuation of study drug/PK assessments from baseline to Week 12.
- Change in Hb concentration from baseline to Week 12.

2.3.2 Secondary Endpoints

- PK analysis of serum iron, corrected serum iron, TSAT, TIBC, transferrin UIBC, maltol and maltol glucuronide in children and adolescents aged 1 month to 17 years in the ferric maltol group.
- Changes in iron markers from baseline to Week 4.
- Changes in iron markers from baseline to Week 12.
- Achieving Hb concentration within normal range at Week 12.
- Qualitative assessments from subject questionnaires that allow evaluation of the acceptability, palatability and ease of use.
- For subjects aged 1 month to < 2 years; maltol and maltol glucuronide in urine from both PK days in children aged 1 month to less than 2 years.

3 STATISTICAL METHODOLOGY

3.1 General Considerations

3.1.1 Analysis Day

Analysis day will be calculated from the date of first dose of study drug in treatment phase. The day of the first dose of study drug will be Day 1, and the day immediately before Day 1 will be Day -1. There will be no Day 0.

Analysis day will be calculated as:

Date of assessment – date of first dose of study treatment + 1 (if date of assessment ≥ date of first dose of study treatment).

3.1.2 Analysis Visits

Scheduled visits will be assigned to analysis visits as recorded on the case report form (CRF). The record occurring on the target day will be picked for analysis. If the record on a target day does not exist, then the one closest to the target date will be used. Unscheduled and early termination visits will be assigned to analysis visits according to the following visit windows:

Analysis Visit	Target Analysis Day	Low Analysis Day	High Analysis Day
Day 1	1	NA	NA
Day 7-10	7	2	17
Day 28	28	18	42
Day 56	56	43	70
Day 84	84	71	No upper limit

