7.5 INDIVIDUAL DISCONTINUATION CRITERIA

Subjects and/or their parents or guardians have the right to withdraw consent without prejudice at any time during the study. If a subject withdraws consent, the Investigator should make a reasonable effort to determine the cause. All withdrawn subjects should have a Post-Treatment Safety Visit within 10-14 days after the last dose of study drug (if the subject agrees in the case of withdrawn consent).

If there is any sign of accumulation of maltol or glucuronide in the pre-assignment phase PK day for subject population aged 1 month to less than 2 years, the recruitment to this age group will be suspended and they will not enter the treatment phase until the risk has been assessed and approved via a substantial amendment to the protocol.

Subjects may be discontinued prematurely during the study for the following reasons:

- Withdrawal of informed consent
- A drop of >1 g/dl in Hb from baseline
- Unwillingness or inability to comply with protocol requirements
- Pregnancy or not using a reliable method of birth control (female subject of childbearing potential)
- Use of prohibited concomitant medications
- Serious adverse events that are judged by the Investigator to be related to study treatment

CONFIDENTIAL Page 47 of 80

- Blood transfusions for any cause during the study treatment period
- Use of any other single agent prescribed iron medications
- Occurrence of any condition that, in the opinion of the Investigator, significantly
 jeopardizes the wellbeing and safety of the patient, including any intolerable toxicity
 related to study treatment determined by the investigator to be unacceptable given
 the severity of the event

The reason for study drug discontinuation and the date of last dose should be recorded in the eCRF. Subjects who discontinue treatment prematurely must return for the Post-Treatment Safety Visit, unless informed consent is withdrawn (and the subject and/or their parents or guardians do not agree to attend this follow-up visit). A subject who meets discontinuation criteria should be discussed on an individual basis with the Medical Monitor.

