10 STUDY PROCEDURES

10.1 COVID-19 IMPLICATIONS ON THE TRIAL

All efforts will be made by the Investigational sites to avoid screenings of any subjects who might have a known exposure to SARS-CoV-2 or any symptoms suggestive of any infection with it by following the local guidelines provided for evaluating patients for COVID-19.

If there is a confirmed COVID-19 positive case (SARS-CoV-2-RT-PCR) in a subject after randomization, the subject will be assessed by the investigator to determine if their participation in the trial is suitable. Positive cases will be recorded as an adverse event in the CRF, and authorised medication will be recorded as concomitant medication in the CRF.

[figure not shown]
Every attempt will be made to follow up with the adverse events via phone call to the subject until known resolution or stabilization of the disease.

During periods of time when a pandemic impedes the ability of patients to travel to the study site

- Study assessments and visit window may be expanded up to 14 days (Visit 4, 5, 6)
- Study assessments by a healthcare professional may occur at an offsite location such as the patient's home.

Where applicable country and local regulations and infrastructure for home healthcare allow, home healthcare may take place at a location other than the clinical trial site to perform study assessments, which may include but are not limited to collection of blood and urine samples, measurement of vital signs, length/height, and weight.

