11.2 REPORTING AND DOCUMENTATION

AEs should be documented in terms of a medical diagnosis. When this is not possible, the AE should be documented in terms of signs and/or symptoms observed by the Investigator or reported by the subject at each study visit.

Any pre-existing conditions or signs and/or symptoms present in a subject prior to the start of the study should be recorded on the Medical History CRF.

All SAEs that occur after informed consent through to study completion (Follow-up visit) or premature discontinuation must be reported on the SAE form in the CRF and reported within 24 hours to the Sponsor using the Shield SAE form. All AEs occurring from the time of the first dose of study treatment through study completion (Follow-up visit) or premature

CONFIDENTIAL Page 67 of 80

discontinuation must be reported on the AE form in the CRF. For AEs related to COVID-19 testing, see section 10.1.

Any SAE that occurs during the clinical study or within two weeks of receiving the last dose of study drug, whether or not related to the study drug, must be reported to the Sponsor.

Deaths or congenital abnormalities if brought to the attention of the Investigator AT ANY TIME after cessation of study drug AND considered by the Investigator to be possibly related to study drug, should be reported to the Sponsor.

At each visit AEs will be solicited. The nature of each event should be established. Details of changes to study drug dosing or any subsequent treatment should be recorded on the appropriate pages of the CRF.

AEs already documented in the CRF (i.e., at a previous assessment) and designated as 'ongoing' should be reviewed at subsequent visits as necessary. Upon resolution, the date of resolution should be recorded in the CRF. If an AE increases in frequency or severity during a study period, a new record of the event should be started. If the AE lessens in intensity, no change in the intensity is required as only the worst intensity must be reported.

All AEs and SAEs, including those that are ongoing at the end of the study or at premature discontinuation, will be followed up until resolution or stabilisation or until the event is otherwise explained.

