2 STUDY OVERVIEW

2.1 Study Objectives

2.1.1 Primary Objective

- To compare the safety and gastrointestinal tolerability of ferric maltol oral suspension and ferrous sulfate oral liquid in children and adolescents aged 2 years to 17 years, and assess the safety and tolerability of ferric maltol oral suspension in children 1 month to less than 2 years, in the treatment of iron deficiency anaemia during the 12 weeks treatment period.
- To assess the effect on haemoglobin (Hb) in children and adolescents aged 1 month to 17 years after twice daily ferric maltol oral suspension administration for 12 weeks.

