- 8. Eligibility laboratory sampling/assessments must be completed before the subject is randomised and before the first dose of study treatment taken. A minimum number of 18 subjects must be recruited into each age group (2 yrs -9 yrs, 10 yrs-17 yrs) and a minimum of 25% of either sex must be recruited and at least 49 subjects per arm.
- 9. Subjects who have at least one dose of study medication and withdraw earlier from the study undergo Visit 7 (Day 94-98) assessments (excluding those who have withdrawn consent).
- 10. Visit 7 is conducted by telephone, unless the Subject has an ongoing AE that requires physical examination or investigations for assessment/management. Visit 7 will take place 10-14 days after Visit 6 (Week 12) unless subject discontinued treatment early. All withdrawn subjects should undergo Visit 7 within 10-14 days after the last dose of study drug (if the subject agrees in the case of withdrawn consent).
- 11. Visit Windows: Maximum of 21 days between screening and randomisation. The Subject must visit to complete:
 - a. Visit 2 and Visit 3: must be 6-9 days between the scheduled PK days.
 - b. Visit 4: +/- 5 days relative to date of Visit 2/first dose administered
 - c. Visits 5 to 6: +/- 5 days relative to date of Visit 2/first dose administered
 - d. Visit 7: 10-14 days after Visit 6 (unless subject discontinued treatment early see Note 10.

Table 2.2: Schedule of Assessments for subjects aged 1 month to <2 years.

	SCREENING	PRE-ASSIGNMENT		TREA	MT	ENT		FOLLOW- UP				
Duration	Up to 21 days	Up to 28 days from Screening	100 mm mm		1 1 1 1 1 1 1 1 1 1 1 1 1 1 1 1 1 1 1		(equivalent		(equivalent of 8			10-14 days
Day			1	7-10	28	56	84	94-98				
Visit ^a	1	Pre-assigned•	2	31	4	5	6	744				
Informed Consent	Х											
Eligibility 1-7	Х	Х	Х									
Demographics	х											
Medical History	Х											
Physical Examination	х						х					
Vital Signs ²	Х	Х	х	х	х	х	х					
Clinical Laboratory tests 4	Х						Х					
Haematology, Iron markers 5	х		Хъ	9			х					
PK assessment: Blood Sampling for iron markers, maltol and maltol glucuronide				Χε								

PK assessment: Urine sampling for maltol/maltol glucuronide		Хе		Хе				
Treatment Assignment 7			Х					
Dispense Study Drug		Х	Х	Х	х	Х		
Return Study Drug for Accountability				Х	х	х	х	
Adverse Events		х	х	х	х	х	х	х
Concomitant Medications and Procedures	х	х	х	х	х	х	х	х
Compliance reminder			х	х	х	х	х	
Compliance assessment	2			Х	Х	Х	Х	

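### The SAP's Week 12 window is open-ended for unscheduled and early-termination Hb, and the exclusion of values after transfusion, IV iron or ESA is stated for the secondary endpoints but not for the primary Hb test

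*SAP*

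**What the plan says.** The second primary objective (SAP 2.1.1) is the effect on Hb "after twice daily ferric maltol oral suspension administration for 12 weeks". SAP 3.1.2 decides which record represents each visit. Scheduled visits keep their CRF label. For the rest, "Unscheduled and early termination visits will be assigned to analysis visits according to the following visit windows". The Day 84 row runs from Day 71 to "No upper limit". Within a window a target-day record is taken; otherwise, "If the record on a target day does not exist, then the one closest to the target date will be used". No precedence is given to a scheduled visit, and no condition is set on time since last dose or on other treatment.

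The schedule in SAP 2.2.1 allows "Visits 5 to 6: +/- 5 days relative to date of Visit 2/first dose administered", so Visit 6 may fall on Days 79 to 89. Protocol 10.1 lets Visits 4 to 6 widen by up to 14 days when a pandemic impedes travel.

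SAP 3.4.1 (primary Hb, MMRM on the mITT population) adds no on-treatment or post-rescue rule. SAP 3.4.2 removes measurements after transfusion, IV iron or an ESA, but under the secondary endpoints. SAP 3.6.2 has haematology taken at Visit 7 in children who discontinued early, and the schedule places that visit 10 to 14 days after the last dose.

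**The concern.** The primary efficacy test is within-arm: the ferric maltol Hb change is compared with zero (SAP 3.1.5). No control difference absorbs a rise that has another cause. If a child's Week 12 value comes from a late sample taken after a transfusion or other iron, the rise counts as ferric maltol efficacy.

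The two SAP sections also treat the same blood sample differently. An Hb taken after IV iron is barred from the secondary normal-Hb rate, yet may enter the primary model.

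The interim test uses the same endpoint and decides whether recruitment stops. SAP 2.2.4 counts withdrawn children towards the 32 that trigger it, so early stoppers can be in those data.

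**Working it through.** **1. The plan's own figure.** Inputs from SAP 2.2.4: n = 49, mean change 0.5 g/dL, SD 1.2, two-sided 5%. Noncentrality = 0.5 × √49 / 1.2 = 2.917. Normal approximation: Φ(2.917 − 1.96) = 83.1%. Noncentral t on 48 df: 81.5%. The stated power of at least 80% is reproduced.

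**2. Displacement of a valid Visit 6.** Visit 6 on Day 79 is |79 − 84| = 5 days from target. An unscheduled repeat on Day 86 is |86 − 84| = 2 days away. The repeat is used.

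**3. Planned discontinuation blood that can reach the window.** With Visit 7 at 10 days after the last dose, the sample falls on Day 71 or later if the last dose was on or after Day 61; at 14 days, on or after Day 57. Assume stopping is uniform over Days 1-83 and occurs at 13% (the 87% adult completion in the protocol synopsis):
- Early stoppers: 49 × 0.13 = 6.37.
- Share reaching the window: 23/83 = 0.277 (10 days) or 27/83 = 0.325 (14 days).
- Expected number: 6.37 × 0.277 = 1.8 to 6.37 × 0.325 = 2.1. At 5% stopping it is 0.7-0.8; at 20%, 2.7-3.2.

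This count holds only if Visit 7 is treated as an early-termination visit, which the SAP does not say. It counts off-treatment values, not values after other iron.

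**4. Size of an upward error (assumed).** The range per child is 1.75 g/dL (2.25 − 0.5, where 2.25 is the adult between-group difference in Protocol 5.4.1) to 3.0 g/dL (a child at −1 scored as +2). Shift in mean = k × error / N. The upper-tail error is for a true zero change, from a simulated one-sample t-test with SD 1.2 for the other children and the sample SD re-estimated each time (400,000 runs).

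| N, two-sided level | k | Shift in mean (g/dL) | Upper-tail error |
|---|---|---|---|
| 49, 5% | 0 | 0 | 2.5% |
| 49, 5% | 1 | 0.036 to 0.061 | 3.6% to 4.2% |
| 49, 5% | 2 | 0.071 to 0.122 | 5.2% to 6.9% |
| 32, 3.45% (interim) | 0 | 0 | 1.7% |
| 32, 3.45% (interim) | 1 | 0.055 to 0.094 | 2.7% to 3.0% |

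**5. The other direction.** With 2 of 49 shifted by −1 g/dL and a true mean change of 0.5, the mean becomes 0.46 and power falls from 81.5% to 73.6%. Shifted by +1, they become 0.54 and 86.2%.

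These are calculations for a simple mean and only approximate the MMRM.

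**The case against.** A reader might infer that treatment failures will routinely be scored as gains: Protocol 7.5 lists "A drop of >1 g/dl in Hb from baseline" as a ground for stopping, and Protocol 11.2 says adverse events "will be followed up until resolution or stabilisation or until the event is otherwise explained", so these children would seem the likeliest to have later Hb checks. The documents do not support that chain. Protocol 10.8.1 exempts low Hb from ongoing iron deficiency from follow-up to resolution. Protocol 11.1.1 leaves the studied disease and its expected progression out of adverse events unless more severe than expected. Protocol 10.8.1 also makes the central laboratory transfer the source for the data, so a later local Hb has no stated route in. Planned contact ends 10 to 14 days after the last dose. By the protocol schedule Visit 7 is normally a telephone call without haematology; only SAP 3.6.2 adds it for early discontinuers.

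Two limits on size also stand. The 2.25 g/dL figure is an adult difference over 12 weeks, so the upward errors above are a stress case, not what a two-week gap would produce. And a reader who held the SD at 1.2 while adding such outlying values would get 6.0-10.4% for two of 49; the outliers raise the SD, and the simulated range is lower.

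Using off-treatment values is a legitimate treatment-policy choice, and SAP 3.4.1 has a per-protocol sensitivity analysis. But the SAP declares no such strategy, its secondary-endpoint rule points the other way, and a per-protocol analysis does not alter the primary result or the interim decision.

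**Conclusion.** The gap is real. The Day 84 window is open-ended, an unscheduled record can displace a valid Visit 6, and the only exclusion after other anaemia treatment stops short of the primary endpoint. For the normal-Hb rate, that exclusion already covers transfusion, IV iron and ESA; what remains there is other oral iron and off-treatment values.

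The effect is probably modest. If one or two of 49 children are affected with large upward errors, the mean moves by 0.04 to 0.12 g/dL (7% to 24% of the assumed 0.5) and the upper-tail error is about 4-7% instead of 2.5%. The number, size and direction are all assumptions. Stopping drug without other iron biases the mean downwards, so the documents do not show that the rule favours ferric maltol overall. They show that the Week 12 value is not tied to the stated objective.

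**What to change.** Before database lock, amend the SAP as follows.

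1. In the Day 84 row of 3.1.2, replace the open upper end with Day 98 (Day 84 plus the protocol's largest visit allowance of 14 days). This keeps the planned discontinuation blood of a child who stops before Day 84: 83 + 14 = Day 97. Scheduled Visit 6 values keep their CRF label.
2. State that a scheduled Visit 6 value takes precedence over any unscheduled value.
3. In 3.4.1 and 4.1, apply the 3.4.2 exclusion (after transfusion, IV iron or ESA) to the primary Hb analysis and the interim test, and extend it to other single-agent oral iron, which Protocol 7.4.1 already prohibits. List the excluded values and repeat the primary analysis with them included.
4. State whether Visit 7 in an early discontinuer is an early-termination visit, and report the primary analysis with and without off-treatment values.

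A rule admitting only values within 5 days of the last dose is not advised. It would discard the discontinuation Hb that SAP 3.6.2 plans at 10 to 14 days and lean on the MMRM's missing-at-random assumption. Step 3 relies on that assumption to a smaller degree, which is why the analysis with those values included is needed.

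The cost is a few lines of text and perhaps one or two fewer Week 12 values. By the t-test calculation, power is 80.7% at n = 48 and 79.9% at n = 47, against 81.5% at n = 49.
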